**Webinar:**

After randomization, participants will complete a 30-minute orientation webinar to learn how to participate. The purpose of the webinar is to educate participants about what research is, review study procedures, review importance of participation of enrolled participants, and to allow participants another opportunity to evaluate if joining this study is the right choice for them. This webinar is being conducted to improve study retention and help inform participants about the study procedures.

In the sun safety condition, they will learn about the Skin Smart Campus Initiative and its audience, how to create effective social media posts, and the type of content that would disqualify a post (e.g., one that promotes tanning or depicts the tanned appearance as desirable since these would undermine a sun safety message). We will inform them that they do not have to reveal their identity in the post, but they may use pics of themselves engaging in sun safety if they so choose. They will be informed that if other people are depicted in their post, they will need to get written permission from those people. We will show them examples of appropriate posts. Participants can choose to either have staff pick a time for their post to go out or they can pick the time themselves. We will give them the timeframe that they can choose from if they wish to do so. If two participants select the same day and time, we will notify the second participant selecting that time slot that another post is scheduled for that time and she/he will be asked to pick a new time slot. Releasing two posts at the same time can result in both posts getting less engagement.

In the healthy lifestyle through technology condition, they will receive the same information except they will learn about the @UConnmHealth feed and its audience. We will inform them that posts should promote the use of technology to engage in healthy lifestyle behaviors including healthy diet, exercise, sleep, meditation, stress reduction, and any topic relating to physical or mental health.

**Intervention:** Participants will be given the name of the feed where their posts will appear. The feeds will be public which means others may follow and content can be shared by other users not in the study. Every Monday participants will be reminded via text message to create their post for the following week and send it to the study team by Friday. They will be given access to a shared calendar to indicate their preferred day/time to for their post to appear. When a post does not meet the guidelines, we will reply to the participant with feedback and encourage them to resubmit an edited version. Participants will receive \$10 Amazon gift card per post for a maximum of 6 posts. Additionally, the participant whose post receives the most engagement, defined as likes, retweets, and replies within the first 48 hours of posting each week will receive \$50 Amazon gift card. The majority of engagement on a social media post occurs within 48 hours. The 48 hour time limit also allows all posts put up by Friday to have a 48 hour period of engagement before the week is over. Winners will be announced via email every Monday.

**Follow-Up Assessment:** Following the intervention period, participants will receive an email (in week 5) with a link to the follow-up survey which will assess indoor tanning, outdoor tanning, intention to tan indoors and outdoors, desirability of tanning and tanning alternatives, exercise and diet quality, social media use, use of health technologies, and acceptability.

*[Describe study procedures for use of interviews or focus groups if applicable. Include details such as how long each procedure will take to complete, who will be asked to participate in these procedures and where these procedures will be conducted. Provide copies of interview and focus group questions/topic areas.]*

*[If the study includes measures, survey instruments and questionnaires (including the collection of demographic data), identify each and, if available, provide references for the measures. Describe what they intend to measure (relate to purpose/hypothesis) and their psychometric properties (e.g., reliability and validity). Identify any that were specifically created for the study and attach a copy for IRB review.]*

**Measures:**

Data collected	List of Measures	Baseline	Intervention	Follow-up	Method
Demographics	Age, gender, sexual orientation, income, employment, marital status, race/ethnicity, household composition, location	X			REDCap
Tanning behavior and sun protection	Tanning behavior and sun protection	X		X	REDCap
Intentions to Tan	Intentions to Tan	X		X	REDCap
Use of tan alternatives	Use of tan alternatives	X		X	REDCap
Exercise and dietary quality*	Block 2005 Food Frequency Questionnaire	X		X	

Social media use (by platform)	Survey questions	X		X	
Use of health technologies	Health Wearable and Health App Usage Questions	X		X	
Recruitment and Retention	Number of responses, eligible, consented participants, % participants who unfollow, % who complete follow-up	X		X	REDCap
Acceptability	Survey questions			X	REDCap
Persuasive impact for each message	Transportation Scale Short Form			X	REDCap
Engagement and dissemination of intervention messages	Engagement in feeds (likes/reactions, comments/replies)		X	X	Twitter and Facebook

*\* Will be added to the measures attachment when it is purchased.*

*[If applicable, describe the use of audiotape and/or videotape, provide justification for use and indicate if this is a requirement of participation.]*

*[If the study involves use of deception or incomplete disclosure, explain the reason why this is necessary to answer the research question(s). Complete the alteration of consent section below]*

*[Describe opportunities provided to participants to ask questions in order for them to make an informed decision regarding participation.]*

Participants will review an informational page before completing the initial survey screener. The participants have the option to end the survey at any time. At the beginning of the telephone screening, staff will review the informational page and ample time will be allowed for discussion or questions.

**Data Analysis:** *[For all studies, specify the analytic techniques the researcher will use to answer the study questions. Indicate the statistical procedures (e.g. specific descriptive or inferential tests) that will be used and why the procedures are appropriate. For qualitative data, specify the proposed analytic approaches.]*

We will use information on recruitment yield, rates, and retention to inform the recruitment strategies and timeline for the subsequent large efficacy trial. Using t-tests, we will compare the two conditions on acceptability, persuasive impact, engagement, and content dissemination. We will also describe changes from baseline to follow-up in desirability of tanning and alternatives, outdoor tanning, intentional tanning outside, sunburns, and sun protection in the two conditions.

**Inclusion/Exclusion Criteria:** *[List ALL inclusion and exclusion criteria. Any proposed exclusion criterion based on gender (women of childbearing potential), age, or race must include justification for the exclusion.]*

Inclusion criteria: 1) Ages 18-30, 2) tanned indoors or outdoors  $\geq 1$  in the past year, 3) likelihood of indoor or outdoor tanning this summer  $> 4$  on a scale from 0-10), 4) regular user of any social media platform.

Participants will be excluded if they:

1. Do not have a smartphone;

2. Do not use a social media platform daily;
3. Did not tan indoors or outdoors at least 1 time in the past year
4. Likelihood of indoor or outdoor tanning this summer is 4 or less on the scale of 0-10
5. Older than 30
6. Younger than 18
7. Does not live in a state with an averages temperature >75 degrees in May (Must live in one of these states: California, Arizona, Oklahoma, Texas, Alabama, Arkansas, Florida, Georgia, Kentucky, Louisiana, Maryland, Mississippi, North Carolina, South Carolina, Tennessee, Virginia, West Virginia, Kansas, Missouri, Delaware, Hawaii);
8. Did not complete the screening procedures;
9. Are unable to provide consent due to mental illness or a cognitive impairment;
10. Does not speak English; or
11. Are a prisoner

*[Describe the conditions under which participants may be removed from the study, i.e., noncompliance with study rules, study termination, etc.]*

Participants will be withdrawn from the study if: they drop from participation or do not complete all screening procedures. Participants reporting that they would like to withdraw from the study will be given the option to withdraw from the study completely with no additional study contact.

***Potential Harms/Risks and Inconveniences:*** *[Describe the potential risks to participants (and secondary participants, if applicable) and steps taken to minimize risks for each participant population. Assess the likelihood of the risk occurring and, if it were to occur, the seriousness to the participant. Types of risks to consider include, but are not limited to: physical, psychological, social, legal, employment, and financial.*

Possible risks for being in this study includes release of confidential information. Tracking data will be stored electronically in REDcap, a network secure data entry program; any data on paper will be stored in a locked file cabinet; and participants will be informed that they may withdraw from the study at any time if they feel discomfort with any of the study procedures. All text messages that was sent and received between staff and participants will be deleted off of the phone at the end of the intervention. All participant phone numbers will also be removed from the study phone after the intervention ends. Any privacy-related problems will be brought to the attention of the PI immediately.

The Twitter and Facebook feeds will be public, which means others may follow it and content can be shared by any Twitter user. Status as a study participant will not be made known on the feeds. Engagement on the intervention posts will be continuously collected, stored for analysis, and monitored using computer programming and will address any issues related to privacy. A staff member will read and assess each interaction with the study feed on a daily basis. Any privacy-related problems will be brought to the attention of the PI and Co-I's immediately.

*[Describe any anticipated inconveniences the participants may experience (such as: their time, abstention from food, etc.).]*

**Benefits:** *[Describe anticipated benefits to the individual participants. If test results will be provided, describe and explain procedures to help participants understand the results. If individual participants may not benefit directly, state so here. Do not include compensation or earned course credits in this section.]*

Participants may experience a benefit of reduced skin cancer risk and a healthier lifestyle

*[Describe anticipated benefits to society (i.e., added knowledge to the field of study) or a specific class of individuals (i.e., athletes or autistic children).]*

Societal benefits include providing evidence to support an intervention delivery modality to help reduce indoor tanning rates and skin cancer.

**Risk/Benefit Analysis:** *[Describe the ratio of risks to benefits. Risks to research participants should be justified by the anticipated benefits to the participants or society. Provide your assessment of anticipated risks to participants and steps taken to minimize these risks, balanced against anticipated benefits to the individual or to society.]*

The possible risks of the study are minimal and are outweighed by the possible benefits to participants. Societal benefits include providing evidence to support an intervention delivery modality to help reduce indoor tanning rates and skin cancer.

**Economic Considerations:** *[Describe any costs to the participants or amount and method of compensation provided. Describe how you arrived at the amount and the plan for compensation; if it will be prorated, please provide the breakdown. Experimental or extra course credit should be considered an economic consideration and included in this section. Indicate when participants will receive compensation.]*

Economic burden to subjects includes the time needed for screening and study participation. There is no cost to participants for participating in the study. Depending on smartphone data usage plan for each participant, usage charges may incur due to increased use of texting as well as Twitter and Facebook mobile apps.

Participants will receive \$10 in compensation per post for up to 6 posts. They will also have a chance of receiving \$50/week for the post that receives the most amount of engagement. Participants will receive \$50 for completing the follow-up survey. Additionally, we will provide participants \$25 at the end of the study if they referred friends and/or family members who ended up being eligible and/or completing the study. All compensation will be in the form of an emailed Amazon gift card.

**Data Safety Monitoring:** *[This is a prospective plan set up by the study investigators to assure that adverse events occurring during studies are identified, evaluated, and communicated to the IRB in a timely manner. Although the investigators initially propose a Data Safety Monitoring Plan (DSMP), the IRB must approve the plan and may require revision of the plan. A DSMP is required for all human studies at the University of Connecticut except for studies reviewed under the Exempt Criteria. For studies that present more than minimal risk to participants, the IRB will review and determine on a case-by-case basis whether a data safety monitoring board is most appropriate. Please refer to the IRB's policy regarding data safety monitoring before completing this section - <http://research.uconn.edu/policies-procedures>.*

Issues that should be addressed in the DSMP include the following:

1. Frequency of the monitoring.
2. Who will conduct the monitoring (Under UConn policy a student cannot be the sole person responsible for monitoring the data and safety of the protocol procedures?)
3. What data will be monitored (include compliance with approved IRB protocol?)
4. How the data will be evaluated for problems?
5. What actions will be taken upon the occurrence of specific events or end points?
6. Who will communicate to the IRB and how will communication will occur?
7. Describe procedures to inform the sponsor.

*Sample response to issues listed above for minimal risk/slight increase over minimal risk – “Survey results will be monitored by the PI in conjunction with the student investigator once every two weeks (items 1, 2 and 3). Survey responses will be reviewed to monitor for clarity (i.e., the same question is skipped by 5 or more participants). In that case, the question will be revised and an amendment will be submitted to the IRB (items 4, 5 and 6).”*

A DSMP will be set up for this study and will convene after it is completed. DSMP reports will be produced by the program director and data manager. Reports will be reviewed by the principal investigator and a statistician then will be sent to the safety officers on the board.

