**Study design:**

Overview: Participation starts with an initial survey, telephone screening, and baseline survey. Eligible participants will then be randomized to one of two conditions, complete a webinar, 4-week intervention, and an end-of-study follow-up survey.

About the intervention: During the 4-week intervention, participants will be asked to create social media posts (related to the topic of the condition). These posts will be sent to the study team who will post them in our study-lead Twitter and Facebook feeds. The sun safety challenge posts will be posted in the Skin Smart Campus Initiative feed and the healthy lifestyle through technology challenge posts will be posted in the @UConnmHealth Feed.

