No. There would not be harm to participants if identification of participants or their responses would place them at risk of liability or be damaging to financial standing, employability, insurability, reputation, or be stigmatizing. The participants are informed that they do not have to answer any questions or interact with any portion of the Twitter or Facebook feeds if it makes them feel uncomfortable in any way is free to stop participating at any time. Participants will be invited to follow the study Twitter and Facebook feeds. They will also be asked questions in the surveys regarding demographics, tanning, impact of the messages, and their acceptability of the Twitter feed, as can be seen in the measures section. None of these measures would negatively impact their financial standing, reputation, employability, or insurability. They are also informed they do not have to respond any survey questions if they do not wish to answer. The ability to review the consent online prior to the survey limits any risks of travelling to the study site for in-person consent. During the telephone screening, we ask for permission to ask questions and indicate that they may choose not to answer.

- Would the signed consent form be the only record linking the participant to the research? Relate this to the procedures to protect privacy/confidentiality.

No. We will use approved institutional data security procedures to protect this information.

- Does the research include any activities that would require signed consent in a non-research setting? For example, in non-research settings, normally there is no requirement for written consent for completion of questionnaires.

No.

- Describe if the participants or their legally authorized representatives are members of a distinct cultural group or community in which signing forms is not the norm, the research presents no more than minimal risk of harm to subjects and there is an appropriate alternative mechanism for documenting that informed consent was obtained. Not applicable to FDA Regulated Studies.

N/A

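### Do the protocol's t-tests on engagement and dissemination, which set one public feed against another, call for a change to the plan?

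*Protocol*

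**What the plan says.** The protocol's Data Analysis section plans: "Using t-tests, we will compare the two conditions on acceptability, persuasive impact, engagement, and content dissemination". The Study design section gives each arm a separate outlet: "The sun safety challenge posts will be posted in the Skin Smart Campus Initiative feed and the healthy lifestyle through technology challenge posts" go to the @UConnmHealth feed. The Webinar section refers to a readership for each. In the sun safety arm "they will learn about the Skin Smart Campus Initiative and its audience"; in the other arm "they will receive the same information except they will learn about the @UConnmHealth feed and its audience". The Intervention paragraph adds: "The feeds will be public which means others may follow and content can be shared by other users not in the study". The request to waive signed consent says only: "Participants will be invited to follow the study Twitter and Facebook feeds".

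The Aim paragraph counts likes and replies as engagement, and retweets, shares and impressions as dissemination. The Measures table has one combined row for engagement and dissemination of the intervention messages, but its contents name only likes or reactions and comments or replies.

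The SAP contains no t-test. It describes post engagement and persuasive impact, and compares acceptability, retention and participation with benchmarks above 80%. Its between-condition tests (Wilcoxon and chi-squared) are on perceived change in motivation, intentions to tan outdoors, times tanned outside, and any outdoor tanning at follow-up.

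**The concern.** Randomisation balances the people who write the posts. It does not balance the people who read and react to them. With one feed per arm, open to the public, some of the engagement probably comes from users who were never randomised. A larger or livelier following on one feed would then appear as a difference between conditions.

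If the protocol's t-test were run and reported without comment, a small p-value could be taken to mean that one kind of message engages young adults better. The Data Analysis section says that the pilot's recruitment and retention information will inform a later efficacy trial, so a misreading of message appeal might be carried forward too. The tests also sit awkwardly with the Justification of Sample Size, which defends 30 per group by citing advice for pilots that propose no inferential results. Finally, shares and impressions are named outcomes with no explicit place in the contents of the Measures row or in the SAP.

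**Working it through.** **Inputs.** Two arms of 30, so 2 × 30 = 60, which agrees with the N in the Aim. There is one feed set per arm (Study design). The documents give no alpha, standard deviation, follower count or impression count. Two-sided 0.05 is assumed below.

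**1. Can condition and feed be separated?** Write the model as y = b0 + b1·condition + b2·feed. Because feed = condition for every participant, the two columns have correlation 1.0 and the matrix [1, condition, feed] has rank 2 with 3 columns. Only b1 + b2 can be estimated. Changing the unit of analysis from participant to post does not alter this.

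**2. What is b1 + b2?** It is the difference between the two interventions as delivered, that is, topic plus feed. The Aim compares one social media intervention with another, and the feed is part of each. The contrast is therefore defined and legitimate. Only the narrower message effect b1 is out of reach, and neither document claims to estimate it.

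**3. What would the t-test do if the feeds differed and message content had no effect?** Let the feeds differ by d standard deviations. The noncentrality is d·√(30/2) = 3.873·d on 58 degrees of freedom.

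| Assumed d | Noncentrality | Probability of p < 0.05 |
|---|---|---|
| 0 | 0 | 0.05 |
| 0.2 | 0.77 | 0.12 |
| 0.5 | 1.94 | 0.48 |
| 0.8 | 3.10 | 0.86 |
| 1.0 | 3.87 | 0.97 |

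Every d here is an assumption. As statements about message content, the rejections at non-zero d would mislead. As statements about topic plus feed, they are ordinary power to detect a real difference.

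**4. Is the test in the analysis?**

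| Outcome | Protocol, Data Analysis | SAP |
|---|---|---|
| Acceptability | t-test | Benchmark above 80% |
| Persuasive impact | t-test | Descriptive |
| Engagement | t-test | Descriptive |
| Content dissemination | t-test | Not named; no test |

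Four outcomes with a t-test in the protocol become none in the SAP. The three benchmarked outcomes (retention, participation, acceptability) do not use engagement counts.

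**5. Where does dissemination go?** The Measures row carries dissemination in its title, so the SAP's post engagement may be meant to cover that row. The Intervention paragraph does count retweets as engagement ("engagement, defined as likes, retweets, and replies within the first 48 hours of posting each week"), but that wording sets the rule for the weekly prize. It is not an outcome definition, so it does not contradict the Aim. What is missing is a statement that shares and impressions are also summarised.

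**The case for a change.** The strongest case for a change is that the aliasing is a certain fact of the design, that no passage warns the reader about it, that a named outcome has no stated analysis, and that the cure is a few words. An impression count beside the raw counts would also help a reader judge the two feeds.

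Much of this stands. Condition and feed coincide exactly, the protocol and SAP differ, and shares and impressions are not explicitly placed. Three things weaken it.

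- The harm needs a test that the SAP does not contain, read in a way that neither document proposes.
- The documents say less about the counts than the concern needs. The risk section speaks of engagement on the intervention posts, so the counts need not cover everything on the feed. No passage says how far the two audiences overlap.
- Deleting engagement and dissemination from the protocol sentence would not reconcile the documents. The t-tests on acceptability and persuasive impact would still be unmatched. So would the SAP's condition tests on tanning intentions and outdoor tanning, where the protocol plans only to describe changes in tanning. Aliasing is no argument for or against those.

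**Conclusion.** The observation is right, but it does not call for a change. For engagement and dissemination, a difference between arms can only be read as topic plus feed. The SAP already treats post engagement descriptively, so no p-value invites the wrong reading. The protocol's t-test sentence is superseded wording, and the place of shares and impressions is missing detail that an analyst fills with a descriptive line. Editing the text would leave the 30 per group, the over-80% benchmarks, the SAP's tests and the feasibility conclusion as they are.

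This rests on two assumptions: that the SAP, written in the past tense as an account of what was done, governs the reported analysis, and that any figures shown by arm are presented as description. The size of any audience difference is unknown, so the rejection probabilities above illustrate the mechanism and are not evidence that the feeds differ.
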